5. TREATMENT OF SUBJECTS

e. Investigational product/treatment

In the United States, only the FDA approved TICE® BCG (for intravesical use) BCG LIVE strain of the BCG (Merck) vaccine or a saline placebo will be administered. This will be given intradermally (0.1mL) in the deltoid area. We are NOT using the BCG Vaccine USP which is also the Tice strain of BCG as it is indicated for the prevention of *Mycobacterium bovis*, at a

different dose, following a different preparation and by means of a different route of administration.

In Houston, randomization will also occur 1:1. (Block randomization discussed below) Placebo vaccine will be 0.1 mL 0.9% NaCl, which is the same amount and color as the intervention.

We remain open to guidance from the FDA and IRBs regarding utilizing additional strains of BCG (eg Russian Strain (Verity), Tokyo Strain (JBL), as they might become available and as necessary). However, we confirm that no other forms of BCG will be administered without IRB and FDA approval. As of 3 April 2020, only the BCG Tice strain will be used in the United States.

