4. INVESTIGATIONAL PRODUCT

a. Name and description of investigational product(s)

Participants that are randomized in the active arm will receive BCG vaccine, the FDA-approved TICE® BCG (for intravesical use) BCG LIVE strain in the United States.

b. Summary of findings from non-clinical studies

BCG has been shown to have the ability to train the innate immune system in an in vitro and in vivo setting. eg. when human monocytes are incubated for 24h in vitro with BCG and after a week are re-challenged with another (part of a) pathogen, the cytokine production is increased, compared to non-BCG trained monocytes.[13] BCG also protects in experimental models of viral infections (e.g. influenza) in murine models.¹³

c. Summary of findings from clinical studies

BCG vaccine has been shown to induce training of the innate immune system in vivo, just as heterologous effects of the adaptive immune system (e.g. increased cytokine production by monocytes and lymphocytes of BCG-vaccinated individuals), which is thought to have a protective effect in countries with a high infectious pressure (e.g. most third world countries).^{17,18} After vaccination with BCG, immune cells isolated from healthy individuals react with an increased production of proinflammatory cytokines after stimulation with both specific (MTB) and non-specific (bacterial, viral, fungal) stimuli. Adolescents vaccinated with BCG have shown a 70% decrease in the incidence of respiratory tract infections compared to placebo⁹. In a small Indonesian trial, consecutive BCG vaccination for 3 months reduced the incidence of acute upper tract respiratory infections by 80% (95%CI=22-95%).[7]

d. Summary of known and potential risks and benefits

The potential benefit for subjects randomized to the BCG-arm is that administration of the vaccine could prevent SARS-CoV-2 infection and lower risk on developing severe illness caused by SARS-CoV-2.

Potential risks include only the well-known side effects of both the vaccines. A short summary of the most common side effects includes: discomfort at the injection site, scarring at injection site, fevers, nausea, vomiting. Severe but very uncommon side effects are: neurological symptoms such as injection site abscesses, BCG lymphadenitis, disseminated BCG diseases, osteitis, osteomyelitis, anaphylaxis, formation of keloid/lupoid, suppurative lymphadenitis. A complete list of known side effects can be found in the information product insert.

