Subjects that receive the placebo hardly have any potential risks and no benefits. Local hematoma formation can occur at the site of vena puncture.

e. Route of administration and dosage

The TICE® BCG (for intravesical use) BCG LIVE strain will be administered in the upper arm slowly (deltoid area), in about 10 seconds, intradermally 0.1ml of the suspended

vaccine, which accounts for approximately 0.075mg of attenuated *Mycobacterium bovis*. The administered 0.1 mL of reconstituted TICE® BCG (for intravesical use) BCG LIVE strain vaccine is approximately 2×10^5 CFU.

Placebo: Administer at the left upper arm slowly, in about 10 seconds, intradermally 0.1ml of 0.9% NaCl solution.

g. Preparation and labelling of Investigational Product (IP)

Preparation and labelling of the investigational products are performed according to GMP guidelines.

In the United States, TICE® BCG (for intravesical use) BCG LIVE strain will be purchased from Merck and reconstituted and prepared according to the package insert/per the approved prescribing information and will include:

- a) preparation using aseptic technique during reconstitution as stipulated in the prescribing information for TICE BCG (for intravesical use) BCG Live.
- b) that reconstituted TICE® BCG should be kept refrigerated (2–8°C), protected from exposure to direct sunlight, and used within 2 hours of reconstitution.
- c) Unused solution should be discarded after 2 hours.
- d) Intact vials (prior to reconstitution) of TICE BCG should be stored refrigerated, at 2–8°C (36–46°F).

Merck sells and distributes 1×10^8 CFU of TICE® BCG (for intravesical use) BCG LIVE strain in a lyophilized (freeze-dried) powder and this will be reconstituted in 50 mL of preservative-free saline, yielding 2×10^6 CFU/ mL. Administration of 0.1 mL will contain $\sim 2 \times 10^5$ CFU, similar to the quantity of BCG vaccine administered worldwide.

The TICE® BCG (for intravesical use) BCG LIVE strain format of the BCG vaccine available in the United States comes in quantities of 1×10^8 CFU per vial and must be used within 2 hours of reconstitution).

h. Drug accountability

Drug accountability will be done in compliance with each pharmacy per their local standard operating procedures and institutional requirements and dispensed from each local pharmacy's supply.

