7. STUDY PROCEDURES

a. Recruitment, Randomization, treatment allocation, and blinding

A standardized, IRB approved email will be sent to department chairs describing the study. A research coordinator will reach out to interested participants via phone with the help of an IRB-approved verbal script to introduce the study, confirm eligibility and provide further instructions on how to access and sign the IRB-approved ICD via REDCap using their own electronic devices. It is important that we obtain the consent via REDCap to a) avoid direct person-to-person contact and comply with social distancing imposed recommendations, and b) minimize the waste of reconstituted BCG by allowing the research personnel to schedule vaccinations in a controlled fashion.

A person under investigation for COVID is not eligible, as per eligibility criteria. To further prevent risk of nosocomial transmission in case of asymptomatic shedding, consenting and screening will occur electronically and over telephone and the intervention will occur at a designated research location away from patient care. If a study participant develops symptoms of COVID19 after enrollment in the study, they will be tested for COVID19 like any other health care worker or community member, and under the supervision, provisions and regulations of their institution and followed per protocol.

Patient registration into the trial will happen immediately after consent has been provided and will involve entering of baseline information into an electronic data capture system (RedCap).

Once the eligibility is confirmed and the ICD signed by the participant and stored in REDCap, the research coordinator will randomize the participant and communicate the treatment assignment to the nurse administering the vaccination. The nurse will subsequently assign an appointment and communicate date and time of vaccination with the participant. All eligible participants will receive intradermal injections of BCG:placebo in a 1:1 ratio.

Both participants and investigators will be blinded to the treatment assignments during the study. However, in case of an emergency where it is important to know the treatment received, the investigator and/or participant can reach out to the unblinded study personnel who will provide the unblinded data. All participants will receive their treatment allocation at the end of the study, after the data analysis is finalized.

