Unblinded personnel will not be involved in the collection and analysis of study data other than the baseline eligibility criteria.

The end of the study is defined as the last patient's last entry in the electronic data capture system.

Informed Consent and Eligibility

The following types of procedures will be conducted as indicated below:

Medical history will be obtained from patient medical record/clinical chart. Informed Consent will be obtained to access these records. When information cannot be obtained or is not available from the patient medical record/clinical chart, it will be obtained via patient interview.

Visual examination will be conducted solely to look for existing BCG vaccination scars.

Symptom evaluation will be conducted via an electronic survey administered to participants every 7 days.

Height, weight, HIV status **and pregnancy** status will be collected as self-reported information. If unknown, a urine pregnancy test will be performed.

Nasopharyngeal, oral and/ or rectal **swabs** will be collected for rt-PCR test for SARS-CoV2 infection if a participant develops symptoms consistent with Covid-19.

If a participant does not know their PPD/IGRA status from within the last 24 months (all health care providers should have this information), an IGRA can be performed to evaluate eligibility.

Study participants have the option of donating blood via phlebotomy (for serological test for Covid-19 disease and PBMCs for immune correlates) or providing a fingerstick and dried blood spot (for serologic test for Covid-19).

Data will be collected at four time points/periods: (1) after consent, (2) at baseline, (3) during follow-up period, and (4) at study end.

Data to be collected during screening includes medical history, visual exam results, results of rt-PCR and serological test results.

Data to be collected during baseline enrollment includes eligibility confirmation, demographic information, risk factors, randomization assignment, confirmation of BCG vaccination/placebo, any immediate reactions to BCG vaccination/placebo. Subjects may also be asked to share a picture of just the injection site. Sharing the picture of the injection site is optional and will not be available to blinded staff members until the end of the study.

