Participants will complete intermittent surveys via an electronic system every 7 days to assess the presence of any flu-like symptom, including sore throat, fever, headache, malaise, and cough. Note that this is part of routine surveillance for Covid-19 in health workers at the United States site. Consent forms will ask for consent to access this survey information.

Any positive response on the survey will trigger a nasopharyngeal, oral and/ or rectal swab to be collected to test for Covid-19 via rt-PCR

All participants, regardless of survey responses, will have serology for Covid-19 tested at 4 week intervals during the follow-up period (6 months)

If a participant completes the follow-up period and does not test positive for disease, their study participation is complete

If a participant does test positive for disease, their disease status will be ascertained for up to two months or until an outcome is available through one of the following mechanisms: (1) an electronic survey if they are not admitted to the hospital, including questions about the number of days they are ill, daily fever, and other symptoms; or (2) if they are admitted to the hospital, ordinal outcomes for disease severity will be extracted from the hospital's electronic medical records system.

During the first week of follow-up, all participants will actively be asked about any adverse events; thereafter, participants will report unsolicited AEs through the electronic survey. Vaccine related adverse events will be graded using the FDA guidance (<https://www.fda.gov/media/73679/download>) and noted using WHO-recommended Adverse event following Immunization forms (AEFI; <https://vaccine-safety-training.org/classification-of-aefis.html>).

Participants will have the option of donating 12 mL of blood for plasma (serology) and PBMCs for secondary analysis of immune correlates and for future analysis based on covid19-specific IgM and IgG. If they do not donate 12mL of blood, a fingerstick will be required for baseline COVID19 serology.

Dried Blood Spot (DBS): all participants will self-collect DBS samples at week 4, 8, 12, 16, 20 and 24. Envelopes to store the DBS are provided upon enrollment and can be mailed or dropped off at work and picked up by study coordinators.

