Although BCG vaccination almost always causes local reactions, serious or long-term complications are rare. Almost all recipients of BCG will experience vaccine site erythema and development of a small pustule. Slight tenderness at the puncture site may be encountered as well as some itching. The initial skin lesions usually appear within 10–14 days and consist of small red papules at the site. The papules reach maximum diameter (about 3 mm) after 3 to 4 weeks, after which they may scale and then slowly subside.

Theoretically it is feasible that a HCW BCG vaccinated could shed attenuated live BCG and transmit this to an immunocompromised patient. While theoretically feasible, we found no case reports of such events. Further, the ability to keep the vaccine site covered is an exclusion criterion. Study participants will be notified of the expected pustule formation and the need to keep it covered by gauze and clothes during the period it is draining. Before the pustule drains, it has characteristic fluctuant appearance and should be covered with gauze from the time fluctuance develops.

iii. Expected rare, serious Adverse events:

Approximately 1 in 1000 to 1 in 10,000 will experience suppurative lymphadenopathy including moderate axillary or cervical lymphadenopathy and induration and subsequent large pustule formation. While local usually resolved within 3-4 weeks, supportive lymphadenopathy can persist for as long as 3-6 months after vaccination. There is not definitive management for suppurative lymphadenitis and treatment will be managed on a case by case basis with some undergoing “watchful surveillance and others drained with incision and drainage. All adverse events will be discussed by the site and overall PIs.

More serious local reactions include ulceration at the vaccination site, regional suppurative lymphadenitis with draining sinuses, and caseous lesions or purulent draining at the puncture site. These manifestations might occur up to 5 months after vaccination and could persist for several weeks. The intensity and duration of the local reaction depends on the depth of penetration of the multiple puncture device and individual variations in patients' tissue reactions.

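### Participant blinding is unlikely to outlast the BCG skin lesion, and the rt-PCR endpoint in 6.a depends on self-reported symptoms; the seroconversion route in 10.c would remove most of the resulting bias but conflicts with 6.a

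*Combined protocol and SAP*

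**What the plan says.** - **Blinding.** Section 7.a: "Both participants and investigators will be blinded to the treatment assignments during the study".
- **Placebo.** Section 5.e: "Placebo vaccine will be 0.1 mL 0.9% NaCl, which is the same amount and color as the intervention". No other matching is described.
- **Lesion.** Section 9.b.ii: "Almost all recipients of BCG will experience vaccine site erythema and development of a small pustule". Lesions usually appear at 10–14 days and are largest at 3 to 4 weeks. Participants are warned of the pustule and told to keep it covered. No comparable reaction to saline is described.
- **Endpoint.** Section 6.a defines the primary endpoint as rt-PCR-confirmed infection. Section 10.c reports it as PCR positivity or seroconversion.
- **Route to a PCR result.** Section 7.c, on the 7-day electronic survey: "Any positive response on the survey will trigger a nasopharyngeal, oral and/ or rectal swab to be collected to test for Covid-19 via rt-PCR". The listed symptoms are sore throat, fever, headache, malaise and cough. Section 7.a adds that symptomatic participants are tested under their own institution's rules.
- **Serology.** Sections 3.a, 7.c and 10.a schedule dried blood spots at weeks 4, 8, 12, 16, 20 and 24. Section 7.c says serology is done whatever the survey shows.
- **Existing protection.** Section 7, on injection-site photographs: "Sharing the picture of the injection site is optional and will not be available to blinded staff members until the end of the study".
- **Injection site.** Section 4.e gives a side for placebo, "Placebo: Administer at the left upper arm slowly, in about 10 seconds, intradermally 0.1ml of 0.9% NaCl solution", but only the deltoid area for BCG.

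**The concern.** A participant who has been told to expect a pustule, and then does or does not get one, can make a good guess at the arm. Under 6.a that same participant decides, by ticking or not ticking mild and subjective symptoms, whether a swab is taken. Someone who believes they are protected may report less; someone who believes they had placebo may report more, and the opposite is also possible. Either way, the chance that an infection becomes a counted event can depend on the arm, and the PCR comparison then mixes efficacy with detection.

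The plan has no check on whether blinding held, no comparison of swab rates by arm and no analysis on serology alone. The secondary endpoint is exposed too: severity is assessed among those who test positive, so unequal detection of mild cases changes its denominator. Section 10.a also sizes the trial on symptomatic COVID-19 and plans Kaplan-Meier curves of COVID-19 disease, both of which depend on symptoms.

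**Working it through.** **Inputs from the documents.** 700 per arm; 5% expected to develop symptomatic COVID-19 (read here as the placebo rate); relative risk 0.4; two-sided alpha 0.05 (all 10.a); maximum follow-up 168 days (3.a); lesion onset at day 10–14 (9.b.ii).

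**Assumed.** The detection ratio r, which is the probability that an infection is detected in the BCG arm divided by that in the placebo arm. The documents give no value, so a range is shown.

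**1. The plan's own figure.** For 5% v 2%, the pooled two-proportion formula needs 588 per arm for 80% power (653 with continuity correction). The stated 700 per arm gives about 86%, or 87.8% by exact enumeration of the same test. The 1400 is not reproduced but is not too small, and this point does not depend on it.

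**2. Exposed follow-up.** (168 − 14)/168 = 91.7% and (168 − 10)/168 = 94.0%. So about 92–94% of maximum follow-up comes after lesions usually appear.

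**3. PCR-only endpoint (6.a), no true effect.** Observed BCG rate = 5% × r. Chance that the pooled z exceeds 1.96 in favour of BCG, by exact binomial enumeration at a single look:

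| r | Expected detected cases, BCG v placebo | False claim of benefit |
|---|---|---|
| 1.0 | 35 v 35 | 2.5% |
| 0.9 | 31.5 v 35 | 6.5% |
| 0.8 | 28 v 35 | 14.6% |
| 0.7 | 24.5 v 35 | 28.7% |

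At r = 0.8 the distortion is seven undetected infections among 700 people. The bias can also run the other way: at r = 1.25 with no true effect, a false finding of harm occurs in 17.3%.

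**4. PCR or seroconversion (10.c).** Let q be PCR detection in the placebo arm and s the serology sensitivity, taken as independent of PCR. The net ratio is [1 − (1 − rq)(1 − s)] / [1 − (1 − q)(1 − s)]. Take r = 0.8, with assumed q of 0.5 to 0.9 and s of 0.80 to 0.95.

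- Worst corner (q = 0.9, s = 0.80): (1 − 0.28 × 0.20)/(1 − 0.10 × 0.20) = 0.944/0.980 = 0.963.
- Best corner (q = 0.5, s = 0.95): (1 − 0.60 × 0.05)/(1 − 0.50 × 0.05) = 0.970/0.975 = 0.995.

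With the placebo rate kept at 5%, the enumeration in step 3 gives a false claim of benefit of 3.7% and 2.7% at these two ratios, against 14.6% for PCR alone.

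**The case against.** The strongest reply is that 10.c already counts seroconversion and that serology is taken from everyone regardless of symptoms, so a planned primary analysis has a route that does not depend on reporting. That stands, and step 4 shows how much it helps. It does not close the matter. Section 6.a still defines the endpoint by rt-PCR alone, so the plan does not commit to the protected definition, and 10.g describes serology as still under development.

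It also stands that differential reporting is a possibility, not something the documents show. The survey is described as part of routine health-worker surveillance, and any one of five common symptoms leads to a swab.

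A reader might infer four stronger things that the documents do not support.

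- **Vaccine fever costs substantial power.** Section 4.d lists "discomfort at the injection site, scarring at injection site, fevers, nausea, vomiting" among the common effects, but with no rate or duration. If infections are spread evenly over 168 days, doubling BCG-arm detection for one week gives r = (168 + 7)/168 = 1.04, and power at relative risk 0.4 goes only from 88% to 86%. Reaching r = 1.2 would need 2.2-fold detection through the first 4 weeks (1 + 0.2 × 168/28), and r = 1.5 would need fourfold.
- **The investigators see routine pustules.** The sentence "All adverse events will be discussed by the site and overall PIs" closes the suppurative lymphadenopathy paragraph in 9.b.iii, which covers rare, serious events. The common small pustule is in 9.b.ii. Staff blinding has some protection from electronic follow-up and the withheld photographs.
- **The injection arm reveals the product.** Nothing says BCG is given on the other side. This is a gap in wording, not demonstrated unblinding.
- **Injection-site adverse events should be withheld from site staff and investigators.** That would conflict with the management, SAE-reporting and halting provisions in 9.b.iii, 9.b.v and 9.d.

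**Conclusion.** The point holds for participant blinding and the 6.a endpoint. By the protocol's own account, blinding of participants is unlikely to last beyond about week 2, and a PCR-only endpoint triggered by self-reported symptoms is then open to detection that differs by arm. The illustrated inflation (2.5% to 6.5% at r = 0.9, to 14.6% at r = 0.8) rests on the assumed ratio, 700 per arm, a 5% placebo rate and a single look. Under the 10.c definition it falls to about 3.7% or less at r = 0.8, if serology sensitivity is 0.80–0.95, independent of PCR, and samples are well returned.

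It would go too far to conclude that the trial cannot be interpreted, or that the bias has a known size or sign. Imperfect masking is hard to avoid with a saline comparator, and the data that limit its effect are already being collected. This should be fixed, and the analysis rules must be set before unblinding to be credible.

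**What to change.** 1. Reconcile 6.a with 10.c so that the primary endpoint is PCR positivity or seroconversion throughout.
2. In 10.c, pre-specify before unblinding an infection analysis by arm using only the scheduled week 4–24 dried blood spots. Show it beside the primary result, and state that a PCR benefit it does not support will be reported with that qualification.
3. Report by arm the share of surveys with any symptom and the number of swabs per participant, with the first 4 weeks shown separately.
4. Make the injection-arm wording in 4.e identical for BCG and placebo.
5. Restate 7.a to say that participant blinding is not expected to persist once lesions appear, and add one treatment-guess item to the final electronic survey.

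**Cost.** Protocol wording, one survey item, and extra tabulations and one extra analysis of data already collected. The blinding claim becomes less favourable. The serology analysis depends on participants returning self-collected samples and on assay accuracy.

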6. STUDY PARAMETERS/ENDPOINTS

a. Primary study endpoint

Incidence of rt-PCR-confirmed SARS-CoV2 infection following BCG vaccination compared to that following placebo.

b. Secondary study endpoint

In individuals who test positive for Covid-19, the proportion with severe disease following BCG vaccination compared to placebo, as defined by the following necessary care levels: non-hospital care; patient hospitalized but no oxygen required; hospitalized and oxygen required; patient treated in intensive care and/or on mechanical ventilation; patient died.

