- Additionally, any serious adverse events that occur after the 30 day time period, or protocol specific timeline, that are related to the study treatment must be reported to the IRB Office.

c. Data Safety Monitoring Board

Safety oversight will be provided by a DSMB. The DSMB consists of 5-7 expert members and are independent of study personnel. The DSMB will consist of members with expertise related to the trial. The DSMB will be run via teleconference with the following current members: [name] (pulmonologist, BCM), [name] (infectious disease physician, BCM), [name] (oncologist and immunotherapy expert, MD Anderson), [name] (infectious disease physician, BCM) and [name], an expert in mycobacterial infections and statistical design and evaluation. If these existing members are unable to participate, they will be replaced with another member with similar expertise. The DSMB will review study collected data and events every month including enrollment, demographics, compliance, adverse events. The DSMB can also meet ad hoc in the event of an unanticipated SAE. The DSMB independent study statistician, [name], will have access to unblinded study data to evaluate these criteria. A final data review meeting will occur two to four months after study completion to review the cumulative safety data. Additional data can be requested by the DSMB as they deem requisite. The DSMB may share de-identified reports with participating/collaborating sites and/or institutions.

d. Halting Rules

The DSMB or study PI may halt the study in for the following reasons:

- Two or more participants develop anaphylaxis
- Three or more participants develop disseminated BCG or suppurative lymphadenitis
- Three or more participants develop disseminated BCG-ititis

- Any participant experiences a serious unexpected adverse event that could be related to vaccination
- A 5% increase in severe COVID19 related illness (severe pneumonia, respiratory failure, ARDS, sepsis, septic shock) among those vaccinated compared to those that received placebo

e. Annual safety report

In addition to the expedited reporting of SUSARs, the Investigator will submit, a summary of safety reports to their IRB, annually, per their local policy and institutional guidelines..

f. Follow-up of adverse events

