10. SAMPLE SIZE AND STATISTICAL ANALYSIS

Data will be reported quantitatively. All analyses will be performed from the intention-to-treat principle. Missing data will be dealt with by multiple imputation using the mice package in R.

a. Sample size calculation

The study in the United States will include at least three sites: Houston (BCM and MD Anderson Cancer Center considered as 'one site' due to proximity), Texas A&M University (TAMU), and Cedars Sinai Medical Center (CSMC). TAMU will enroll 1400 individuals. The proposed enrollment sample size is designed to provide 80% power to detect a 60% vaccine efficacy (a relative risk of 0.4 among the vaccinated). This is based on the observed three-fold decline in respiratory infections in the South Africa adolescent cohort with 80% power and 0.05 type 1 error in a two-tailed test. We expect 5% of study participants to develop symptomatic COVID19 during follow-up, therefore a sample size of 1400, with 700 receiving intervention and 700 receiving placebo. We do not expect significant loss to follow up among HCWs (there has been zero LTF after the first 500 participants). We will plot Kaplan-Meier curves comparing COVID19 disease between the BCG and placebo groups and report hazard ratios and p-values using Cox proportional hazard models. DBS samples will be collected at baseline and weeks 4, 8, 12, 16, 20 and 24 post intervention. PBMCs and plasma donations are optional at baseline, 12 and 24 weeks. If interim analysis identifies a large proportion of participants to be seropositive before intervention, power analysis will be evaluated and an amendment will be submitted if additional participants need to be recruited.

b. Interim analysis

One month after the first 100 participants are enrolled, an interim analysis will be held by the independent statistician of the trial. Data will be exported independently from all sites and then data collated and merged for the interim analysis). The above described statistical analysis will be evaluated as well as safety profile. Enrollment is expected to occur within the first two months of launch. Interim analysis will occur based on study enrollment and three to six interim analysis will occur based on temporal dynamics of enrollment as requested by the DSMB. We will stop the clinical trial early if the p-value of any interim analysis is smaller than the pre-specified type-1 error cutoff. Each interim analyses will be reported to the DSMB.

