c. Primary study parameter(s)

The primary endpoint, development of COVID19 infection, we will use the Cox proportional-hazards model to calculate hazard ratios for the development of Covid-19. This will be reported as the proportion of individuals receiving the intervention who are PCR-positive or seroconvert.

d. Secondary study parameter(s)

Disease severity as discussed above and based on guidelines proposed by the World Health Organization. We will use the Chi square for significance to calculate the risk ratios for the development of severe Covid-19 disease. Disease severity will be based on the level of care required for individuals who test positive for COVID19 as follows: non-hospital-based care; patient hospitalized but no oxygen required; hospitalized and oxygen required; patient treated in intensive care and/or on mechanical ventilation; patient died. Additional WHO criteria for severity include severe pneumonia, respiratory failure, acute respiratory distress syndrome, sepsis and septic shock. Days absent will also be self-reported via the RedCap Research App. Immunology and epigenetic studies for innate training be implemented, but in brief, immune cells will be stimulated with non-specific (LPS, mitogen, BCG) and COVID19-specific antigens with immune function measured by ELISA and flow cytometry. Epigenetic studies are discussed in more detail below.

e. Other study parameters

Continuous baseline characteristics will be reported as mean and standard deviation or median and inter-quartile range, as appropriate. Categorical baseline characteristics will be reported as count and percentage. No statistical testing for baseline characteristics will be performed.

f. Synthesis

In this trial, the BCG vaccine will be used in hospital personnel during the epidemics to prevent infection with the new SARS-CoV-2 virus. The risk of the BCG vaccine is very well known (see product inserts) and only minor local side effects (redness, local pain) are common. The benefits of BCG vaccination based on earlier clinical studies are expected to be a reduction in infection and morbidity of at least 25% compared to unvaccinated individuals, and potentially much higher. These effects are mediated by the capacity of BCG to induce trained immunity and may represent an important tool for protection against SARS-CoV-2 virus infection until a specific effective vaccine is developed.

g. Epigenetic and Immune Corollary Studies

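### Section 9.d's 5% halting criterion for severe COVID-19 does not say relative or absolute and sets no minimum count, and neither reading gives a usable threshold

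*Combined protocol and SAP*

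**What the plan says.** Section 9.d (Halting Rules) opens with "The DSMB or study PI may halt the study in for the following reasons". Its last item is "A 5% increase in severe COVID19 related illness", with the severe conditions listed in brackets, "among those vaccinated compared to those that received placebo". It gives no scale for the 5%, no minimum number of cases, and no test or confidence limit. The anaphylaxis and BCG-disease items in the same list are plain participant counts. Neither 9.c (DSMB) nor 10.b (interim analysis) fills the gap.

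The groups named in 9.d are most naturally all recipients in each arm. Section 6.b uses another denominator for the severity endpoint: "In individuals who test positive for Covid-19, the proportion with severe disease following BCG vaccination compared to placebo".

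Section 10.a supplies the sizes: "We expect 5% of study participants to develop symptomatic COVID19 during follow-up", with 700 participants per arm.

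**The concern.** This is the only halting rule that compares severe COVID-19 between the arms. That comparison bears on the hazard raised in section 9.b.iii, that BCG might provoke damaging immune pathology in someone infected later. A numerical threshold should tell the DSMB whether given data meet it. Here the relative and absolute readings can give opposite answers on the same data, even with the denominator settled. One is met by a single extra case. The other stays silent through a doubling of severe disease.

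**Working it through.** **Inputs from the documents.** 700 per arm and 5% symptomatic COVID-19 (10.a); maximum follow-up 168 days (3.a); DSMB review every 4 weeks (9.b.iii) or monthly (9.c); design efficacy 60% (10.a). Section 9.d states no error rate or case count, so there is no figure to reproduce.

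**Assumptions, not in the documents.** Severe share of symptomatic cases 5-20%; six reviews (168 / 28 = 6); everyone at risk from the first review; cases spread evenly. Except where 60% efficacy is stated, incidence is 5% in both arms and any harm changes severity only.

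**Expected cases per arm.** 0.05 x 700 = 35 symptomatic. Severe: 35 x 0.05 = 1.75; 35 x 0.10 = 3.5; 35 x 0.20 = 7.

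**Absolute reading, all recipients.** 0.05 x 700 = 35 excess severe cases, equal to every symptomatic case expected in an arm. Exact binomial chance of reaching this if severe disease doubles: at most 0.002%, for severe shares up to 30%. At five-fold harm it is under 0.002% at shares of 5-10% and 15% at 20%; that last cell assumes every symptomatic BCG case is severe.

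**Relative reading, all recipients.** With k severe placebo cases, one excess case meets the criterion when (k + 1)/k >= 1.05, so k <= 20. At k = 0 the ratio is undefined, and any BCG excess is counted as met. Simulated chance of meeting the criterion:

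| Scenario | Final look only | Any of six looks |
|---|---|---|
| No effect, no efficacy | 39-45% | 55-69% |
| No severity effect, 60% efficacy (35 vs 14 cases expected) | not tabulated | about 25-29% |
| Severe disease doubled, no efficacy | 71-92% | 82-97% |

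**Same data, both readings.** Six severe on BCG, three on placebo:
- Absolute: 6/700 - 3/700 = 3/700 = 0.43 points; not met.
- Relative: 6/3 - 1 = 100%; met.

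**Denominator, a secondary matter.** Suppose 60% efficacy, with 14 infected on BCG and 35 on placebo, and three severe in each arm. Per recipient the arms are equal (3/700 each), so the criterion is not met on either scale. Among cases, 3/14 = 21.4% against 3/35 = 8.6%, so it is met on both.

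**Trial size.** Section 10.a says "TAMU will enroll 1400 individuals", which leaves room for a larger trial across sites. At 1,400 per arm the absolute reading needs 0.05 x 1,400 = 70 excess cases, and the relative reading is met in 63-72% of no-effect trials over six looks. The conclusion does not change.

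**The case against.** Several counter-arguments have force.

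- **The rule only permits a halt.** A reader might infer that most null trials would be stopped under the relative reading. The documents do not support that: the rates above are chances of meeting a criterion, after which the DSMB or PI decides.
- **There are other routes to a halt.** A reader might infer that enhanced disease would otherwise go unchecked. It would not. Section 9.a provides for suspension when subject safety is jeopardised. Another item in 9.d covers any serious unexpected event possibly related to vaccination. SAEs reach the DSMB within 5 working days, and it reviews monthly and can meet ad hoc.
- **The groups are named.** A reader might count denominators among symptomatic or among all infected participants as equally open. The wording of 9.d points to all recipients; section 6.b leaves some doubt but defines an efficacy endpoint. Figures for an all-infected denominator would also need an asymptomatic ratio that the documents do not give.
- **Post hoc choice is conjecture.** A reader might infer that the meaning would be picked after seeing unblinded data. Nothing says so, and the DSMB could settle it beforehand.
- **The false-alarm rate depends on efficacy.** It falls to about 25-29% at the design efficacy.

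These points limit the consequence. They do not supply the missing scale or minimum count, and the relative-absolute conflict persists with all recipients as the denominator.

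**Conclusion.** The criterion cannot be applied as written. At 700 per arm its absolute reading is practically unreachable under a doubling of severe disease, and its relative reading responds to one excess case. The 35-case and one-case figures need only the protocol's sample size. The probabilities also rest on the assumed severe share of 5-20%, the review pattern and the stated efficacy. Six reviews reflects each participant's follow-up; with enrolment over two months the trial would have somewhat more. The practical consequence is limited, given the discretion and the other safeguards. It is still worth correcting, because this is the one rule that compares the arms on this hazard.

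**What to change.** In 9.d, replace the 5% criterion with a one-sided exact binomial boundary on the split of cumulative severe COVID-19 cases between arms, among all randomised participants, at a lenient level such as 0.15 per look. This sets its own minimum: 3 versus 0 gives 0.5^3 = 0.125, while 2 versus 0 gives 0.5^2 = 0.25. Keep the halt discretionary. At each review the DSMB statistician should also report the severe share among infected participants by arm, so that efficacy cannot hide worse disease after infection.

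Over six looks with no efficacy, the 0.15 boundary is met in 8-20% of trials with no effect, 31-72% with doubling and 88-100% with five-fold harm. A 0.05 level (not reachable before 5 versus 0) gives 0.7-5.5%, 9-47% and 65-99.8%.

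**Downside.** With so few severe cases expected, the boundary is less sensitive to modest harm than a one-excess-case rule. Six versus three does not meet it: P(X >= 6 of 9) = 130/512 = 0.25. If BCG prevents infection, the boundary is also less sensitive to harm conditional on infection. At 60% efficacy, five-fold severity is flagged in 31-72% of trials at 0.15 and 9-47% at 0.05, hence the extra report.

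If the sponsor prefers to keep a 5% rule, 9.d should state its scale, denominator and minimum count.

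**Cost.** An amendment to the wording of 9.d and a short calculation. The unblinded DSMB statistician already has access to the data; no new collection or participants are needed.
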